Table 1. Conditions for Withholding and/or Permanent Discontinuation of Amgen Investigational Product and Other Protocol-required Therapies due to Potential Hepatotoxicity

Analyte	Temporary Withholding	Permanent Discontinuation
TBL	> 3x ULN at any time	> 2x ULN
		OR
INR	--	> 1.5 (for subjects not on anticoagulation therapy)
	OR	AND
AST/ALT	> 8x ULN at any time > 5x ULN but < 8x ULN for ≥ 2 weeks > 5x ULN but < 8x ULN and unable to adhere to enhanced monitoring schedule > 3x ULN with clinical signs or symptoms that are consistent with hepatitis (such as right upper quadrant pain/tenderness, fever, nausea, vomiting, jaundice).	In the presence of no important alternative causes for elevated AST/ALT and/or TBL values > 3x ULN (when baseline was < ULN)
	OR	
ALP	> 8x ULN at any time	--

ALP = alkaline phosphatase; ALT = alanine aminotransferase; AST = aspartate aminotransferase; INR = international normalized ratio; TBL = total bilirubin; ULN = upper limit of normal.

6.5.2 Criteria for Rechallenge of Amgen Investigational Product and Other Protocol-required Therapies After Potential Hepatotoxicity

The decision to rechallenge the subject should be discussed and agreed upon unanimously by the subject, investigator, and Amgen.

Approved

If signs or symptoms recur with rechallenge, then Amgen investigational product and other protocol-required therapies, as appropriate, should be permanently discontinued. Subjects who clearly meet the criteria for permanent discontinuation (as described in [Table 1](#)) should not be rechallenged.

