Appendix A. Additional Safety Assessment Information

Adverse Event Grading Scale

Refer to the NCI Common Terminology Criteria for AEs (CTCAE) Version 4.0 for AE grading and information. The CTCAE is available at the following link:
http://ctep.cancer.gov/protocolDevelopment/electronic_applications\ctc.htm.

Pediatric Drug-induced Liver Injury Reporting & Additional Assessments Reporting

To facilitate appropriate monitoring for signals of DILI, cases of concurrent AST or ALT and TBL and/or INR elevation according to the criteria specified in [Section 6.5.1](#) require the following:

- The event is to be reported to Amgen as a serious adverse event within 24 hours of discovery or notification of the event (ie, before additional etiologic investigations have been concluded).
- The appropriate CRF (eg, Event CRF) that captures information necessary to facilitate the evaluation of treatment-emergent liver abnormalities is to be completed and sent to the Amgen.

Other events of hepatotoxicity and potential DILI are to be reported as serious adverse events if they meet the criteria for a serious adverse event defined in [Section 9.1.3](#).

Additional Clinical Assessments and Observation

All subjects in whom investigational medicinal product(s) or protocol-required therapies is/are withheld (either permanently or conditionally) due to potential DILI as specified in [Table 1](#) or who experience AST or ALT elevations > 3x ULN or 2-fold increases above baseline values for subjects with elevated values before drug are to undergo a period of “close observation” until abnormalities return to normal or to the subject’s baseline levels.

Assessments that are to be performed during this period include:

1. Repeat liver tests AST, ALT, ALP, bilirubin (total and direct), and INR within 24 hours.
2. In cases of TBL > 2x ULN or INR > 1.5, retesting of liver tests, BIL (total and direct), and INR is to be performed every 24 hours until laboratory abnormalities improve.
3. Obtain pediatric gastroenterologist or pediatric hepatologist consult.

Testing frequency of the above laboratory tests may decrease if the abnormalities stabilize or the investigational product(s) or protocol-required therapies has/have been discontinued AND the subject is asymptomatic.

- Initiate investigation of alternative causes for elevated AST or ALT and/or elevated TBL. The following are to be considered depending on the clinical situation:

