Appendix D. Tanner Stages (Sexual Maturity Ratings)

The table below or equivalent locally used guidance should be used for the assessment of sexual maturity (Tanner Staging) in this study. The table is adapted from [Lifshitz \(2007\)](#).

FEMALES:

Stage	BREAST	PUBIC HAIR STAGING	CONCOMITANT CHANGES
1	Prepubertal, papilla elevation	No pigmented hair	
2	Budding; larger areole; palpable and visible elevated contour	Pigmented hair, mainly labial	Accelerating growth rate
3	Enlargement of the breast and areola	Coarser, spread of pigmented hair over mons	Peak growth rate, thicker vaginal mucosa, axillary hair
4	Secondary mound of areola and papilla	Adult type but smaller area	Menarche (stage 3 or 4) decelerating growth rate
5	Mature	Adult distribution	

MALES:

Stage	GENITAL SIZE	PUBIC HAIR STAGING	CONCOMITANT CHANGES	PRADER ORCHIDOMETER
1	Prepubertal	No pigmented hair	Long testis axis < 1.5 cm	1 – 3 mL
2	Early testicular, penile and scrotal growth	Minimal pigmented hair at base of penis	Early voice changes; testes length 2.5 – 3.3 cm	3 – 6 mL
3	Increased penile length and width; scrotal and testes growth	Dark, coarse, curly hair extends midline above penis	Light hair on upper lip, acne, maximal growth, testes length 3.3 – 4.0 cm	8 – 12 mL
4	Increased penis size including breadth; pigmented scrotum	Considerable, but less than adult distribution	Early sideburns; testes 4.0 – 4.5 cm	> 12 mL
5	Adult size and shape	Adult distribution, spread to medial thighs or beyond	Beard growth; testes > 4.5 cm	> 15 mL

Approved

Amendment 4

Protocol Title: Open-label, Single-arm, Multicenter Study to Evaluate the Safety, Tolerability and Efficacy of Evolocumab for LDL-C Reduction, as Add-on to Diet and Lipid-lowering Therapy, in Pediatric Subjects From 10 to 17 Years of Age With Heterozygous Familial Hypercholesterolemia (HeFH) or Homozygous Familial Hypercholesterolemia (HoFH)

HAUSER-OLE

Amgen Protocol Number (Evolocumab) 20120124
EudraCT number 2015-002276-25

Amendment Date: 27 May 2020

Rationale:

The following changes were made to the protocol, dated 27 May 2020.

- Added interim analysis for all enrolled subjects
- Updated number of subjects expected to roll over from Study 20120123 into study 20120124 to approximately 111 subjects and 10 subjects with Homozygous Familial Hypercholesterolemia (HoFH) with an expected total enrollment of approximately 124 subjects.
 - Updated Study Schema figure with new enrollment number
- Align with current protocol template:

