9.6.3 Analyses of Secondary Safety Endpoints

Descriptive statistics of change from baseline will be provided for the following safety parameters at week 80.

- Steroid hormone levels (FSH, LH, ACTH, DHEA-S, cortisol, estradiol in females, testosterone in males).
- Carotid intima-media thickness (cIMT)

Summary of subject incidence of abnormal muscle and liver enzymes at week 80 will also be provided.

Abnormalities of muscle and liver enzymes will be assessed by the following categories:

- CK > 5 x ULN
- CK > 10 x ULN
- ALT or AST > 3 x ULN
- ALT or AST > 5 x ULN
- Total bilirubin \geq 2 x ULN
- (ALT or AST > 3 x ULN) and (Total bilirubin > 2 x ULN) and Alkaline Phosphatase < 2 x ULN

Descriptive statistics of change from baseline in growth (height and weight) will be provided at week 24, 48 and 80 by study cohort, parent study treatment and gender.

Shift from baseline in Tanner staging at weeks 24, 48 and 80 will be summarized by study cohort, parent study treatment and gender.

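### The SAP's only combined liver row requires ALP below 2x ULN and has no INR arm, so it can omit a case that the protocol's own DILI rule reports as a serious adverse event

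*SAP*

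**What the plan says.** **SAP 9.6.3** announces the display as follows: "Summary of subject incidence of abnormal muscle and liver enzymes at week 80 will also be provided". It lists six categories: two for CK, two for ALT or AST (above 3x and above 5x ULN), one for total bilirubin at or above 2x ULN, and one combined row: "ALT or AST > 3 x ULN) and (Total bilirubin > 2 x ULN) and Alkaline Phosphatase < 2 x ULN". INR appears in none of them. No reason is given for the ALP condition, and SAP Section 10 declares no change from the protocol-specified analyses.

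**Protocol 6.5.1, Table 1**, permanent-discontinuation column, requires total bilirubin above 2x ULN or INR "> 1.5 (for subjects not on anticoagulation therapy"), together with AST/ALT "> 3x ULN (when baseline was < ULN") and no important alternative cause. The ALP cell in that column is empty. ALP enters the table only for temporary withholding, at above 8x ULN.

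**Protocol Appendix A** makes "cases of concurrent AST or ALT and TBL and/or INR elevation according to the criteria specified in" Section 6.5.1 an SAE, to be reported within 24 hours and before the cause has been worked up. It adds no ALP condition.

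**The concern.** The combined row is where a reader will look for possible serious liver injury in the laboratory data. Its definition is narrower than the protocol's reporting rule in two ways: it adds an ALP ceiling, and it drops INR as an alternative to bilirubin. Either difference alone is enough to exclude a case that the protocol requires sites to report as serious.

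At stake is how a zero in that row is read. Abnormal muscle and liver enzymes are a secondary safety endpoint, and safety is the purpose of the study. With few expected cases, one omission changes the row from some to none. The reader could then meet a liver SAE beside a combined row of zero, with nothing to explain the difference.

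**Working it through.** The plan states no figure for this point, so the check compares the two rules.

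**Inputs**
- Protocol rule (Table 1 and Appendix A): AST/ALT > 3x AND (TBL > 2x OR INR > 1.5). The permanent-discontinuation column is used because it is the only one that requires a transaminase together with bilirubin or INR; the withholding column joins its rows by OR and has no INR entry.
- SAP row (9.6.3): AST/ALT > 3x AND TBL > 2x AND ALP < 2x.
- Held fixed: baseline AST/ALT below ULN, no alternative cause, no anticoagulant.

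**Worked profiles** (multiples of ULN; INR absolute)

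| Profile | Protocol rule | SAP combined row | ALT/AST > 3x row | TBL ≥ 2x row |
|---|---|---|---|---|
| ALT 4, TBL 2.5, ALP 1, INR 1.0 | yes | yes | yes | yes |
| ALT 4, TBL 2.5, ALP 2 or 3, INR 1.0 | yes | **no** | yes | yes |
| ALT 4, TBL 1, ALP 1, INR 1.6 | yes | **no** | yes | no |

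**Grid.** AST/ALT 2, 4, 6; TBL 1, 2, 2.5; ALP 1, 1.9, 2, 3; INR 1.0, 1.6. That is 3 × 3 × 4 × 2 = 72 profiles.
- Meeting the protocol rule: 2 AST/ALT values × 4 TBL–INR pairs × 4 ALP values = 32.
- Also in the SAP row: 2 × 1 TBL value × 2 ALP values × 2 INR values = 8.
- Missed: 32 − 8 = 24. Of these, 2 × 1 × 2 × 2 = 8 fail on ALP, and 2 × 2 × 4 × 1 = 16 have TBL at or below 2x and qualify only through INR.
- All 24 appear in the ALT/AST > 3x row, and 16 of the 24 in the TBL ≥ 2x row.
- No grid profile is in the SAP row but outside the protocol rule.

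These counts are logical profiles, not frequencies.

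**What one omitted case does to the display** (exact binomial)
- All subjects, n about 124: 1/124 = 0.8% (95% CI 0.02% to 4.4%), shown instead as 0/124, with one-sided 95% upper limit 1 − 0.05^(1/124) = 2.4%.
- HoFH, n about 10: 1/10 = 10% (0.3% to 44.5%), shown instead as 0/10, with upper limit 1 − 0.05^(1/10) = 25.9%.

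**Other displays.** SAP 9.6.2 tabulates SAEs by system organ class and preferred term, and its special groupings cover injection-site reactions, hypersensitivity and neurocognitive events, with no liver grouping. SAP 9.6.4 describes summaries of laboratory parameters and a grade shift table for liver tests. Nothing described there shows transaminase and bilirubin or INR raised in the same subject.

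**Timing.** Protocol Table 2 schedules chemistry after day 1 at weeks 12, 48 and 80. In SAP Appendix A the week-80 chemistry window opens after day 448. If 9.6.3 means that window, an earlier case is absent from the row whatever its ALP or INR. If it means cumulatively through week 80, it is not. The text does not settle this.

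**Is INR available?** It is not a scheduled test; Protocol Table 3 refers it to Appendix A. Appendix A requires INR within 24 hours for any subject with AST or ALT above 3x ULN, and the laboratory results of a potential DILI event must be entered in the CRFs. Subjects who could qualify should therefore have a value, though possibly from the repeat draw and not the triggering sample.

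**The case against.** The strongest reply is that the two rules serve different purposes. Table 1 is an individual stopping rule with clinical judgement built in; the SAP row is a descriptive tabulation. Protocol 10.4.3.2 promises only a summary of abnormal enzymes and defines no categories, and INR is not an enzyme. This stands: a reader might infer that the SAP departs from a protocol-specified analysis, and the documents do not support that. What remains is an unexplained mismatch.

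A reader might also infer that the case vanishes from the report. It does not. It should appear in the SAE table, in the ALT/AST > 3x row and, for the ALP route, in the bilirubin row. Only the concurrence is lost.

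A third tempting inference is that pubertal growth raises ALP, so the ceiling would often exclude cases at this age. Protocol Appendix D refers to "Accelerating growth rate" in a Tanner stage but nowhere mentions ALP. The documents also do not say whether the central laboratory's ALP limit is age- and sex-specific; silence is not evidence that adult limits are used. The share of cases excluded could be anywhere from 0 to 1.

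Finally, an INR arm would rest on selectively tested subjects, and a purely laboratory row cannot apply Table 1's conditions on baseline, alternative cause and anticoagulation. Both points stand and are met by the labelling and the listing. For reporting, the alternative-cause condition carries less weight, because Appendix A requires the report before the work-up ends.

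**Conclusion.** The mismatch is plain in the text. The one combined laboratory row can read zero for a case that the protocol reports as an SAE, through ALP at or above 2x ULN or through INR with bilirubin at or below 2x ULN, and no other described display shows the concurrent elevation. The effect on the table is one case at a time: 0 in place of 1 among about 124 subjects, or among about 10 in HoFH. The frequency cannot be estimated from the documents, and a claim of frequent misses would not be supported.

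The conclusion assumes that Appendix A's reference to Section 6.5.1 means the permanent-discontinuation criteria, and that the example subjects meet Table 1's remaining conditions. It says nothing about whether the clinical thresholds are right. The point is modest, and worth acting on because the correction is cheap.

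**What to change.** In SAP 9.6.3 keep the present row and add beside it:

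*(ALT or AST > 3x ULN) and (total bilirubin > 2x ULN or INR > 1.5), concurrent, at any post-baseline assessment, regardless of ALP.*

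- Label it a laboratory screen aligned with the protocol's DILI reporting rule and not identical to Table 1.
- Define concurrent so that the repeat draw under Protocol Appendix A counts, and include unscheduled results.
- List each case with ALP, INR, baseline AST/ALT, anticoagulant use, any alternative cause and Tanner stage.
- State which ULN is applied, and whether it is age- and sex-specific.

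The cost is one row, one listing and two definitions. It needs no new tests and no change to patient management. The downside is that the broader row may include a cholestatic or otherwise explained case, which the listing will show, and that INR is available only for subjects tested under Appendix A, which a footnote should say.

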9.6.4 Laboratory Test Results

Descriptive statistics will be provided for actual values and changes from baseline in select laboratory parameters at select protocol-specified scheduled visit. Laboratory

analytes are provided in the protocol Table 3. CTCAE grading v5.0 or later will be used for lab shift table for liver function test (LFT).

9.6.5 Vital Signs

Systolic and diastolic blood pressure and heart rate will be summarized using descriptive statistics at each scheduled visit.

9.6.6 Physical Measurements

Physical measurements will be summarized using descriptive statistics at each scheduled visit.

9.6.7 Electrocardiogram

For post-baseline assessments where ECG is performed in triplicate, the average of the 3 (or all available) readings will be used for analysis. Observations with the following diagnosis or findings will be excluded from analysis: artificial pacemaker, atrial fibrillation, atrial flutter, left bundle branch block, and right bundle branch block. PR, QRS, QT, QTc and RR intervals and their change from baseline will be summarized by scheduled visit. Subjects will be categorized and summarized per their maximum post-baseline absolute QTc interval using limits of 450 ms, 480 ms, and 500 ms. They will also be categorized per their maximum change from baseline QTc interval using limits of 30 ms and 60 ms.

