7.7.5 Electrocardiograms

At each scheduled visit where ECGs are being obtained ECGs will be performed in a standardized method, in triplicate, and run consecutively (ie, < 30 seconds apart), prior to blood draws or other invasive procedures. Using equipment supplied to each site, all protocol-specified ECGs will be acquired and transmitted to the centralized ECG services provider. The PI or designated physician will review acquired ECGs. One (1) signed, original ECG tracing should be retained with the subject's source documents. At the request of the sponsor, the original ECG should be made available to Amgen to be manually read by a central reader.

The centralized ECG services cardiologists will perform standard interpretations of all tracings. A cardiologist reviewed ECG report will be provided to the study site. Investigators must initial and date the ECG reports upon receipt. If the investigator's interpretation of any protocol-specified or unscheduled ECG differs from that supplied by centralized ECG services provider, it is the responsibility of the investigator to make the final clinical decisions. The investigator's interpretation does not need to be reconciled with that supplied by centralized ECG services cardiologists. Any clinical interventions based on these results need to be documented in the appropriate source documents and CRF as applicable. It is the responsibility of the investigator to obtain additional ECGs required for the clinical management of the subject, using centralized ECG services equipment or equipment on-site.

Further detail about the equipment provided and its use for this study will be provided in an Investigator ECG Manual distributed to the sites before start of enrollment.

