9. SAFETY DATA COLLECTION, RECORDING, AND REPORTING

9.1 Definition of Safety Events

9.1.1 Adverse Events

An adverse event is defined as any untoward medical occurrence in a clinical trial subject. The event does not necessarily have a causal relationship with study treatment. The investigator is responsible for ensuring that any adverse events observed by the investigator or reported by the subject are recorded in the subject's medical record.

The definition of adverse events includes worsening of a pre-existing medical condition. Worsening indicates that the pre-existing medical condition or underlying disease (eg, diabetes, migraine headaches, gout) has increased in severity, frequency, and/or duration more than would be expected, and/or has an association with a significantly worse outcome than expected. A pre-existing condition that has not worsened more than anticipated (ie, more than usual fluctuation of disease) during the study or involves an intervention such as elective cosmetic surgery or a medical procedure while on study, is not considered an adverse event.

An adverse device effect is any adverse event related to the use of a medical device. Adverse device effects include adverse events resulting from insufficient or inadequate instructions for use, adverse events resulting from any malfunction of the device, or adverse events resulting from use error or from intentional misuse of the device.

The investigator's clinical judgment is used to determine whether a subject is to be removed from treatment due to an adverse event. In the event a subject, or subject's legally acceptable representative requests to withdraw from protocol-required therapies or the study due to an adverse event, refer to [Section 8.1](#) for additional instructions on the procedures recommended for safe withdrawal from protocol-required therapies or the study.

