10.1.1.4 Other Safety Endpoints

- Select safety laboratory values and vital signs at each scheduled assessment
- Incidence of anti-evolocumab antibody (binding and neutralizing) formation
- Abnormal neurological examination findings
- ECG parameters (such as RR, PR, QRS, QT, and QTc intervals) at each scheduled assessment
- Change from baseline score in the components of the Cogstate battery at each scheduled administration

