10.4.4 Other Safety Endpoints

All analysis of the other safety endpoints will use the FAS.

Laboratory Parameters

Selected safety laboratory parameters will be summarized using descriptive statistics.

Vital Signs

Vital signs will be summarized using descriptive statistics.

Neurologic examination

The incidence of abnormal neurologic findings overall and in each exam area will be summarized by treatment group.

Cogstate battery

Change from baseline score in the components of the Cogstate battery at each scheduled administration will be summarized using descriptive statistics.

Anti-evolocumab antibodies

The incidence and percentages of subjects who develop anti-evolocumab antibodies (binding and neutralizing) at any time will be tabulated.

ECG

Summaries over time and/or changes from baseline over time will be provided for all ECG parameters.

Subjects' maximum change from baseline in QTcF will be categorized and the number and percentage of subjects in each group will be summarized.

Subjects' maximum post baseline values will also be categorized and the number and percentage of subjects in each group will be summarized.

Approved

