9.6.2 Adverse Events

The Medical Dictionary for Regulatory Activities (MedDRA) version 22.0 or later will be used to code all events categorized as adverse events to a system organ class and a preferred term. Severity of AEs will be graded using the CTCAE ([Appendix B](#)) and recorded on the eCRF.

The subject incidence of adverse events will be summarized for all treatment-emergent adverse events, serious adverse events, adverse events leading to withdrawal of investigational product and fatal adverse events.

Subject incidence of all treatment-emergent adverse events, serious adverse events, adverse events leading to withdrawal of investigational product and fatal adverse events will be tabulated by system organ class and preferred term in alphabetical order.

In addition, summaries of treatment-emergent and serious adverse events occurring in at least 1% of the subjects by preferred term will be provided in descending order of frequency.

Subject incidence of adverse events associated with lipid lowering therapies:

- **Injection site reactions**
- **Hypersensitivity or allergic reactions**

will be summarized by category and preferred term.

Subject neurocognitive events will also be summarized.

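### The SAP drops ECGs with bundle branch block, atrial fibrillation or flutter, or a pacemaker from every interval summary, including QRS, and plans no count of what it drops

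*SAP*

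**What the plan says.** The protocol's ECG endpoint (10.1.1.4) is "ECG parameters (such as RR, PR, QRS, QT, and QTc intervals) at each scheduled assessment". Its planned analysis (10.4.4) reads: "Summaries over time and/or changes from baseline over time will be provided for all ECG parameters". It names no tracing to be left out.

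SAP 9.6.7 adds a filter: "Observations with the following diagnosis or findings will be excluded from analysis: artificial pacemaker, atrial fibrillation, atrial flutter, left bundle branch block", followed by right bundle branch block. The next sentence lists the summaries that follow: "PR, QRS, QT, QTc and RR intervals and their change from baseline will be summarized by scheduled visit". Subjects are then categorized by "maximum post-baseline absolute QTc interval using limits of 450 ms, 480 ms, and 500 ms", and by maximum QTc change at 30 and 60 ms. Nothing ties the filter to QT or QTc, and nothing separates a pre-existing finding from a new one. SAP section 10 reports no change from the protocol-specified analyses.

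On reading the tracings, protocol 7.7.5 says: "The centralized ECG services cardiologists will perform standard interpretations of all tracings". The same section lets the investigator's interpretation differ from the central one without reconciliation.

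**The concern.** A tracing with bundle branch block or an irregular atrial rhythm can give a QT or QTc value that is hard to interpret, so leaving it out of those summaries is ordinary practice. QRS is different. Bundle branch block shows itself as a wide QRS, so dropping those tracings from the QRS summary drops values because of what they show. If a block appears for the first time on evolocumab, the subject leaves both the QRS summary and the QRS change from baseline.

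The SAP also plans no number excluded, no reason for exclusion and no listing of ECG findings. A reader of the study report could not tell whether the ECG tables cover everyone with a tracing, or everyone except those with the findings of interest. In a single-arm descriptive study, where individual cases carry much of the safety information, that is a transparency gap.

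**Working it through.** The documents state no figure on this point, so the check is mainly a comparison of sections.

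**1. Reach of the rule.** All ECG analyses in the SAP sit in 9.6.7: PR, QRS, QT, QTc and RR by visit, their changes, and the QTc categories. The exclusion stands ahead of all of them without qualification.

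**2. Effect on QRS change.** In a group of n subjects, let one have a new block with QRS change d, and let the others have mean change m.
- Mean with the subject kept: ((n − 1)m + d)/n
- Mean with the subject excluded: m
- Shift caused by the exclusion: −(d − m)/n

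If the new block widens QRS, d exceeds m and the reported mean change is too low by (d − m)/n. That is one tenth of the excess with n = 10 and 1/111 of it with n = 111. The maximum would also lose its most informative value. The documents give no d, so no figure in milliseconds follows.

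**3. How much of a subject is lost.** Protocol Table 2 schedules the 12-lead ECG on day 1 and at week 80. SAP Appendix A gives ECG one post-baseline window, from after day 1 to end of study. If every available reading in that window carries the finding, the subject contributes to no post-baseline ECG summary.
- HoFH: 1/10 = 10%
- HeFH: 1/111 = 0.9%

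SAP 5.3 also splits HeFH by parent-study treatment. Within either part the share exceeds 0.9%, but the sizes of the parts are not given.

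**4. Illustrative frequency.** Assume a rate p of new listed findings between 0.5% and 3%. This range is an assumption, and the true rate could be lower. The expected number is np and the chance of at least one is 1 − (1 − p)^n.

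| n | p | Expected | Chance of at least one |
|---|---|---|---|
| 10 | 0.5% | 0.05 | 5% |
| 10 | 3% | 0.30 | 26% |
| 124 | 0.5% | 0.62 | 46% |
| 124 | 3% | 3.72 | 98% |

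The conclusion does not depend on this table.

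**5. Would the finding appear elsewhere?** Protocol 9.1.1 is broad: "An adverse event is defined as any untoward medical occurrence in a clinical trial subject". SAP 9.6.2 has treatment-emergent and serious events "tabulated by system organ class and preferred term in alphabetical order", and the ECG filter is not attached to those tables. A finding recorded as an adverse event is therefore shown. But recording is left to judgment. Protocol 7.7.6 sends clinically significant changes in the physical examination to the adverse event form, while 7.7.5 has no matching instruction for ECG. A new block read centrally and judged unimportant at the site can thus miss the adverse event tables and also be removed by SAP 9.6.7.

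**6. Comparison within the SAP.** Section 9.2 counts exclusions from the full analysis set with reasons, and 9.6.9 tabulates abnormal neurologic findings. ECG has neither kind of output.

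**The case against.** The strongest reply is that 9.6.7 summarizes intervals, not diagnoses. Even with no exclusion, atrial fibrillation or bundle branch block would not be named there; the tables that name them are the adverse event tables, which support the primary endpoint and are untouched. This stands. A reader might infer that new rhythm and conduction abnormalities in general are deleted from the analysis meant to show them. The documents do not support that: five findings are listed, and PR prolongation, other arrhythmias and QRS widening without bundle branch block all stay in.

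A reader might also infer that every ECG result can only look better under the rule. That is not supported either. The direction is clear only for QRS with a new block. Removing a subject with a stable, pre-existing block can move the mean change either way, atrial fibrillation leaves no PR interval to lose, and the direction for RR is undetermined.

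Nor does one affected tracing necessarily remove a subject. ECGs are taken in triplicate, SAP 9.6.7 averages whatever readings are available, and unscheduled ECGs are foreseen.

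It is also fair that a SAP exists to add detail to the protocol, that central reports go to the site for review, that an external monitoring committee reviews accumulating data, and that ECG is an other-safety endpoint in a study with no testing. These points limit the importance. They do not explain why the exclusion extends to QRS, or why the number excluded goes unreported.

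**Conclusion.** The point holds as a targeted defect that should be corrected. The exclusion is sound for QT/QTc. For QRS it is outcome-dependent when the bundle branch block is new, it is absent from protocol 10.4.4, and it is not declared in SAP section 10. With no count or listing planned, a centrally read new finding that the investigator does not record as an adverse event could appear in no planned table.

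The loss per case is at most one subject: 10% of an HoFH cohort of about 10, or 0.9% of about 111 HeFH subjects. This assumes that all of the subject's available post-baseline readings carry the finding. How often that would happen cannot be derived from the documents. The primary endpoint analysis is not affected.

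**What to change.** Amend SAP 9.6.7 and section 10:
- Limit the exclusion to QT and QTc, and to other intervals only where they cannot be measured or interpreted (for example PR in atrial fibrillation, or paced tracings).
- Keep bundle branch block tracings in the QRS summary.
- Report the number of ECGs excluded by visit, cohort and reason.
- List subjects with any of the five centrally read findings post-baseline that were absent at baseline. For rollover subjects SAP 5.2 sets baseline in the parent study, so the listing should state which baseline it uses.
- Record the exclusion in section 10 as a change from the protocol.

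The cost is SAP wording, one count and one listing, all from central ECG readings that the protocol already obtains. No new assessment is needed.
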